6.1 Study Day and Visit Windows

Day 1 is defined as the date of first dose of study treatment. For days on or after the first dose of study treatment:

Study day = non-missing date of assessment/event - date of first treatment + 1

For days before the first dose of study treatment:

*Study day = non-missing date of assessment/event - date of first treatment
(one day prior to date of the first dose will be considered 'Day -1')*

For all analysis populations, all data will be analyzed using nominal scheduled study visits as defined in the SoA, i.e., scheduled visits. The only exception is for clinical safety laboratory evaluations, the analysis of shifts from baseline to worst post-baseline will use all scheduled and unscheduled visits within the study phase.

No visit windows will be applied for summary and analysis.

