7.1 General Principles

Formal statistical hypothesis testing will not be performed.

Analysis of safety data will be presented by the initial combination dose level. Safety analyses will be presented for each cohort separately and for the overall study population. For efficacy analyses will be presented by the initial combination dose level. Efficacy analyses will be presented for Cohort 1 and Cohort 2 separately, and for the overall study population.

All summary tables will include data from scheduled assessments, unless otherwise specified. A final analysis will be performed at the EOS as defined in [Section 2.2.4](#).

Confidence intervals (CI) will be two-sided and will use and 95% coverage, unless specified otherwise.

Subject listings of data (scheduled and unscheduled) from the eCRFs, external source and derived variables will be presented by dose level.

Study Day: In all the subject listings, the study day of all complete dates as defined in Section 5.1 will be presented.

Baseline: Unless stated otherwise, baseline is defined as the last non-missing assessment prior to the first dose of either study drug (RMC-4630 or sotorasib).

SAS® Version 9.4 or higher will be the statistical software package used for all data analysis and presentation.

The Tables of Contents of Tables, listings, and figures (TLFs) a document external to this SAP. Mock of TLF shells will be created in a separate document.

7.1.1 Handling of Data Quality Issues due to Severe Acute Respiratory Syndrome Coronavirus 2 (SARS-CoV-2) and Related Restrictions

Due to Severe acute respiratory syndrome coronavirus 2 (SARS-CoV-2) and related restrictions, there is a high risk for impact to data integrity, with the recognized potential for:

- Missed visits, caused by, for example:
 - Subject unable to travel to site due to restrictions, the need to quarantine, or SARS-CoV-2 infection
 - Subject unwilling to go to site due to fear of SARS-CoV-2 infection
 - Site postponing subject's visit due to investigator not being available (e.g., if they have been dispatched to hospital handling SARS-CoV-2 infections)
- Site unable to replenish supply of investigational product
- Incomplete data entry by sites due to limited resources to support study or no access to source documents or to eCRF
- Unanswered queries

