7.7.1 Analyses of Clinical Safety Laboratory Results

All clinical laboratory evaluations including clinical chemistry, hematology, coagulation and urinalysis, and pregnancy tests will be performed per Protocol SoA.

For each test, baseline is defined as the last non-missing value prior to first dose of the study treatment.

All post-baseline summaries will include results collected on or after the date of the first dose of study intervention and within 30 days of last known dose of study intervention. Shifts from baseline to worst post-baseline CTCAE Version 5.0 or later grade (including unscheduled visits) will be presented by frequency and percentage for select laboratory parameters. For those parameters where worst is an increase or a decrease from baseline, separate summaries will be presented.

Time to onset of and duration of first post-baseline hematologic abnormalities of hemoglobin decreased, platelet count decreased and neutrophil count decrease will be summarized for each grade using descriptive statistics.

Listings of all subjects with clinically significant abnormal results including concurrent elevated ALT $\geq 3 \times$ upper limit of normal (ULN) or AST $\geq 3 \times$ ULN AND bilirubin $> 2 \times$ ULN or ALT $\geq 3 \times$ ULN and concurrent INR > 1.5 at any time post-baseline will be presented over time.

Listings of all laboratory values (hematology, chemistry, coagulation, urinalysis, pregnancy tests, and other screening test results) including results from unscheduled visits will be provided. The

listing will flag all out of normal ranges values and will include change from baseline for each post-baseline measurement (where applicable).

Adverse Events of Clinical Interest (ECI)

Adverse events of Clinical interest are defined based on sponsor pre-defined standardized MedDRA queries (SMQs) extracted using MedDRA preferred terms as listed in RMC-4630 Events of Clinical Interest document.

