7.7.5 Electrocardiograms (ECG) and QTcF Interval

Baseline is defined as the last non-missing measurement on or prior to the first dose of study drug.

The QTcF and ECG overall interpretation (normal, abnormal not clinically significant [NCS], abnormal clinically significant [CS]) will also be summarized for baseline and change from baseline to EOT [expressed as Improvement, No Change, and Deterioration] by dose level, where:

- Improvement = Abnormal CS to Abnormal NCS/Normal or Abnormal NCS to Normal;
- Deterioration = Normal to Abnormal NCS/CS, Normal/Abnormal NCS to Abnormal CS
- No change = Normal to Normal, Abnormal NCS to Abnormal NCS, Abnormal CS to Abnormal CS.

In addition, the QTcF values for baseline, actual values and changes from baseline at each post baseline visit will be summarized by dose level using descriptive statistics.

The frequency and percentage of the maximum post-baseline QTcF values classified in accordance with the ICH E14 boundaries will be presented:

Table 1: QTcF / QTcB Interval ICH E14 Boundaries

QTcF / QTcB Interval	Criteria (msec)
Maximum Observed QTcF / QTcB interval	≤ 450 msec > 450 msec > 480 msec > 500 msec
Maximum Change from baseline in QTcF / QTcB interval	≤ 30 msec > 30 to ≤ 60 msec > 60 msec

A listing of all ECG data including individual and calculated mean of triplicate measurements, derived change from baseline will be provided using the treated population, along with demographic information of age and sex. Any value outside the clinical reference range will be flagged.

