7.7.6 Echocardiograms/Multigated Acquisition Scans

Echocardiogram or multi-gated acquisition results will be presented in a data listing. In addition to descriptive statistics of observed data, the number and percent of subject with LVEF values below 50% will be presented.

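### Read as written, SAP 6.1 keeps unscheduled ECGs out of the maximum-QTcF table in 7.7.5, and probably unscheduled echocardiograms out of the LVEF below 50% count in 7.7.6

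*SAP*

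**What the plan says.** The general rule is in SAP 6.1: "For all analysis populations, all data will be analyzed using nominal scheduled study visits as defined in the SoA, i.e., scheduled visits". The next sentence begins "The only exception is for clinical safety laboratory evaluations" and confines the exception to shifts from baseline to worst post-baseline, using scheduled and unscheduled visits within the study phase. The section ends: "No visit windows will be applied for summary and analysis".

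SAP 7.1 restates the default: "All summary tables will include data from scheduled assessments, unless otherwise specified". Listings are treated differently and cover both kinds of data: "Subject listings of data (scheduled and unscheduled) from the eCRFs".

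Three later sections report a worst value or a threshold count:

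- SAP 7.7.1, laboratory: "Shifts from baseline to worst post-baseline CTCAE Version 5.0 or later grade (including unscheduled visits) will be presented by frequency and percentage".
- SAP 7.7.5, ECG: "The frequency and percentage of the maximum post-baseline QTcF values classified in accordance with the ICH E14 boundaries will be presented". Its table has rows for the maximum observed interval (up to above 500 msec) and the maximum change (up to above 60 msec).
- SAP 7.7.6, ECHO/MUGA: "the number and percent of subject with LVEF values below 50% will be presented".

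Only the laboratory section mentions unscheduled visits.

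**The concern.** A scheduled-visit rule suits by-visit summaries, where one value per subject per visit is wanted. It does not suit a table of each subject's maximum, because a maximum over part of the readings may not be the subject's maximum. The SAP recognises this for laboratory data and does not carry it over to QTcF or LVEF.

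ECG changes are part of the secondary safety endpoint (SAP section 3). The above-500 and above-60 msec rows use the same cut-offs as the prolonged-QTcF definition in protocol 7.1. A reader will take a zero in those rows to mean that no subject crossed the threshold, when it may mean that none crossed it at a scheduled visit. LVEF is not named in that endpoint, so this argument supports the QTcF part only.

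**Working it through.** The plan gives no figure to reproduce. The check sets the passages side by side and then sizes one affected subject.

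**1. Which rule governs each summary**

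| Summary | Default (6.1, 7.1) | Section's own wording | Result |
|---|---|---|---|
| Laboratory shift to worst grade | Scheduled only | Unscheduled visits included (6.1 and 7.7.1) | All readings |
| Maximum QTcF and maximum change | Scheduled only | Silent (7.7.5) | Scheduled only |
| LVEF below 50% | Scheduled only | Silent (7.7.6) | Probably scheduled only |

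With no visit windows, a reading labelled unscheduled cannot be moved to a nearby nominal visit. An early or late reading entered under its nominal visit is still included.

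**2. Whether the protocol produces off-schedule readings**

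- *ECG.* The schedule is triplicates on C1D1 and C1D15, then one pre-dose ECG on Day 1 of every second cycle from Cycle 3, and EOT (Table 1 footnote 13; protocol 8.2.4). From Cycle 3 the on-treatment gap is 2 × 21 = 42 days. Unscheduled visits are allowed at any time (protocol 1.3), further QTcF readings are called for (8.2.4), and ECGs are monitored after an overdose (8.5).
- *LVEF.* The fixed post-baseline assessments are C2D1 and EOT, and the EOT one is generally not required for subjects who do not complete 2 cycles (Table 1 footnote 14). The same footnote adds assessments when clinically indicated, and end-of-cycle ECHOs for 2 more cycles after a dose reduction for LVEF decrease.

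**3. Direction of the error**

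Let A be all of a subject's post-baseline readings and S the scheduled ones, so S is a subset of A. Then max(S) ≤ max(A). With baseline held fixed, the same is true of the maximum change. The counts above 500 msec and above 60 msec from S can therefore equal or fall below those from A, but never exceed them. A subject with a value below 50% in S also has one in A, so the LVEF count behaves the same way.

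**4. Size of one affected subject**

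One subject whose only qualifying value is off schedule changes the percentage by 1/n. Denominators are from SAP 2.3.

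- Overall, n = 46: 1/46 = 2.2 points.
- Expansion dose, n = 40: 1/40 = 2.5 points.
- Expansion dose, n = 20: 1/20 = 5.0 points.

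Neither document gives a basis for estimating how many subjects this would be.

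**The case against.** The strongest reply is that the exclusion is inferred. SAP 7.7.5 never says that unscheduled ECGs are left out, its row label refers to the maximum observed interval, and SAP 6.1 cannot be literal for everything, since adverse events and deaths are not visit-based. A programmer might reasonably use all readings, and the TFL shells or programming specifications, which are not available here, may say so. This limits certainty about what will be produced. It does not rescue the text: 6.1 calls the laboratory exception the only one, and a row label does not override that. At best the SAP is ambiguous on a table where the choice matters.

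For LVEF the reply is stronger. SAP 6.1 refers to visits as the SoA defines them, and footnote 14 of the SoA lists the clinically indicated and post-reduction ECHOs. They are not nominal scheduled visits, but the opposite reading can be argued. A reader might infer that 7.7.6 certainly drops them; the documents do not support that degree of certainty.

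The consequence is also limited. The extra QTcF readings in protocol 8.2.4 are meant to show improvement or resolution, so most follow a prolongation already seen and need not be the maximum. Clinically significant ECG findings meet the AE definition (protocol Appendix 3). Related Grade 3 or higher QTc prolongation in Cycle 1 is a DLT (protocol 8.4). The listings carry unscheduled data. All of this stands and lowers the weight, but none of it corrects the count in the table.

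A reader might also infer from 6.1 that off-schedule scans are lost to the efficacy analyses. The documents do not support that: SAP 7.6.2 calculates DOR and PFS from event and censoring dates, measures the minimum duration of stable disease to the scan date, and refers to a separate censoring document.

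**Conclusion.** The concern holds for QTcF. On the SAP's own wording, the maximum-value and maximum-change table is restricted to scheduled ECGs and can only understate the counts above 500 msec and above 60 msec. For the LVEF below 50% count the same result is probable but less clear.

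It would go too far to say that the reported figures will be wrong or that safety data are lost. An understatement needs a subject whose only qualifying value is off schedule; the number of such subjects is unknown and may be zero; and the readings remain in the listings. Each such subject costs 2.2 points at n=46 and 2.5 to 5.0 points at n=40 to 20.

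The conclusion assumes that 6.1 is applied as written, that the unseen shells and specifications do not depart from it, and, for maximum change, that baseline is the same under either reading. It should be fixed because a stated rule can give a wrong result in a table whose label promises a maximum.

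**What to change.** Keep the laboratory exception in SAP 6.1 unchanged, including its limit to the study phase. Extend it to three further summaries: maximum post-baseline QTcF, maximum change from baseline in QTcF, and the number of subjects with LVEF below 50%. By-visit summaries stay on scheduled visits.

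Add to 7.7.5 and 7.7.6:

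*Including unscheduled assessments, from first dose to within 30 days of the last dose (as in 7.7.1); triplicate ECGs are averaged per time point and unscheduled single ECGs recorded in the eCRF are used as recorded.*

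The time window stops the maximum from being open-ended. The averaging rule settles how single readings sit beside triplicates. The restriction to eCRF records avoids assuming that continuous-monitoring output is captured. The ECG clause is not needed in 7.7.6.

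The cost is minor: a short SAP amendment, with the programming specifications and table shells aligned to it. No new data are needed, because unscheduled eCRF data are already planned for the listings.

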6.2 Handling of Missing Data and Dates of Events

All safety analyses will be conducted on the observed data unless otherwise mentioned. No imputation of values for missing data will be performed except that missing or partial start and end dates of adverse events used for the assessment of treatment emergence status of an AE, study day of onset, and duration of the AE (if applicable) and concomitant medication. Missing and / or incomplete dates for AEs and concomitant medications are imputed in a manner resulting in the earliest onset or the longest duration during the treatment period, whilst ensuring that the start date does not occur after the stop date. The stop date will not be imputed if the AE or concomitant medication is “Ongoing”.

The detailed imputation algorithms will be specified at programming specifications. Refer to [Section 7.6](#) for handling of missing efficacy data.

7. Statistical Methods

7.1 General Principles

Formal statistical hypothesis testing will not be performed.

Analysis of safety data will be presented by the initial combination dose level. Safety analyses will be presented for each cohort separately and for the overall study population. For efficacy analyses will be presented by the initial combination dose level. Efficacy analyses will be presented for Cohort 1 and Cohort 2 separately, and for the overall study population.

All summary tables will include data from scheduled assessments, unless otherwise specified. A final analysis will be performed at the EOS as defined in [Section 2.2.4](#).

Confidence intervals (CI) will be two-sided and will use and 95% coverage, unless specified otherwise.

Subject listings of data (scheduled and unscheduled) from the eCRFs, external source and derived variables will be presented by dose level.

Study Day: In all the subject listings, the study day of all complete dates as defined in Section 5.1 will be presented.

Baseline: Unless stated otherwise, baseline is defined as the last non-missing assessment prior to the first dose of either study drug (RMC-4630 or sotorasib).

SAS® Version 9.4 or higher will be the statistical software package used for all data analysis and presentation.

The Tables of Contents of Tables, listings, and figures (TLFs) a document external to this SAP. Mock of TLF shells will be created in a separate document.

7.1.1 Handling of Data Quality Issues due to Severe Acute Respiratory Syndrome Coronavirus 2 (SARS-CoV-2) and Related Restrictions

Due to Severe acute respiratory syndrome coronavirus 2 (SARS-CoV-2) and related restrictions, there is a high risk for impact to data integrity, with the recognized potential for:

- Missed visits, caused by, for example:
 - Subject unable to travel to site due to restrictions, the need to quarantine, or SARS-CoV-2 infection
 - Subject unwilling to go to site due to fear of SARS-CoV-2 infection
 - Site postponing subject's visit due to investigator not being available (e.g., if they have been dispatched to hospital handling SARS-CoV-2 infections)
- Site unable to replenish supply of investigational product
- Incomplete data entry by sites due to limited resources to support study or no access to source documents or to eCRF
- Unanswered queries

At the time of the reporting of the study results, all protocol deviations due to SARS-CoV-2 or related restriction will be assessed for their severity and impact on the analyses. If needed, appropriate statistical methods will be applied as a mitigating action (e.g., data might be categorized into 2 analysis groups, with and without SARS-CoV-2 and related restrictions impact); however, this will exclude any imputations of the missing values. Any mitigating actions will be agreed with Revolution Medicines, Inc. in advance and identified in the CSR.

7.2 Subject Disposition and Data Sets Analyzed

All subject's disposition data will be summarized for by the initial combination dose level and overall using treated population. The summary will include following:

- number of subjects in each analysis population,
- number of subjects discontinuing treatment with primary reason for treatment discontinuation,
- number of subjects discontinuing study with primary reason for study discontinuation, and
- number of subjects continued to long term follow-up period
- time on study (month) calculated as $(\text{study exit date} - \text{first treatment date} + 1) / 30.4375$, censored using earlier of data cut-off date and death date
- time on each treatment (months) calculated as $(\text{last treatment date} - \text{first treatment date} + 1) / 30.4375$, censored using data cut-off date.

The percentages will be calculated based on total number of subjects in each dose level. The percentages for primary reason for treatment or study discontinuation will be calculated based on total number of subjects who discontinued the treatment and/or the study at each dose level.

Data listing of disposition information will also be provided.

7.3 Protocol Deviations

Important protocol deviations employed in database deviation report that could potentially affect the interpretation of the safety, efficacy, PK, or PD data will be identified by the review team prior to database lock. All Coronavirus Disease of 2019 (COVID-19) related deviations are also recorded in the protocol deviation document.

All major protocol deviations will be summarized by the initial combination dose level and overall using treated population. The count of unique subjects with at least one major protocol deviation as well as the number of subjects in each protocol deviation category will be presented by default descriptive summary statistics for categorical variables.

A listing of all important protocol deviations, including the description of the deviation, deviation category of 'major', and date of deviation will be provided.

In addition, a listing of the subjects affected by COVID-19 and the type of COVID-19 disruption will be provided for the treated population if applicable.

Any additional details will be documented and added prior to database lock.

7.4 Demographics, Baseline Characteristics, Medical History, and Prior/Concomitant Medications

Demographic, baseline characteristics, medical history, and prior/concomitant medications will be summarized by dose level and overall using the treated population.

7.4.1 Demographic and Baseline Characteristics

The demographic and baseline characteristics include, but not limit to the following parameters and will be summarized using descriptive statistics:

All subject's demographic and baseline characteristics will be summarized by dose level and overall using all treated population.

- Age (years)
- Height (cm)
- Weight (kg)
- Body mass index (BMI) (kg/m²)
- Years since initial cancer diagnosis
- Number of previous systemic cancer therapies

The following demographic and baseline characteristics variables will be summarized using count and percentage:

- Age (<=65 or > 65 years)
- Sex
- Age by Sex (Female: <=65 or > 65 years, Male: <=65 or > 65 years)
- Ethnicity
- Race
- Childbearing potential (females only)
- Smoking status (current smoker, past smoker, never smoked)

- Baseline Eastern Cooperative Oncology Group (ECOG) performance status
- PD-L1 expression at study entry
- PD-L1 Expression (TPS <1%, TPS 1% - 49%, TPS >=50%)
- History of CNS involvement
- Disease stage at study entry
- Brain Metastasis at Baseline (Yes/No)
- Liver Metastasis at Baseline (Yes/No)

The summary will also include count and percentage of all subjects with the following genotypic mutations based on the historic genomic reports and ctDNA analysis results collected at baseline:

- Cohort 1: Only *KRAS*^{G12C} (without any potential genetic modifiers)
- Cohort 2: *KRAS*^{G12C} co-occurring with STK11/LKB1, KEAP1, PIK3CA, BRAF Class 1/2/unclassified, ATRX, or BRCA2

Data listing of demographic and baseline characteristics information will be provided.

7.4.2 Medical History

Medical history terms will be coded using the MedDRA® (Medical Dictionary for Regulatory Activities), Version 25.0 or later. Medical history will be summarized by dose level and overall using treated population by system organ class (SOC) and preferred term (PT). For the table summary, a subject will only be presented once for each level of summarization.

Subject listings of medical history, non-cancer related surgical history, and cancer related surgical history will also be provided.

